5.2 Lenalidomide (RevlimidTM)

5.2.1 Lenalidomide Administration and Schedule

Lenalidomide will be given orally. Schedule as shown in table 5.1

The first dose level starts at 15 mg days 1-21 of a 28 day cycle.

If a dose is missed or vomited up, the dose will not be made up.

Beginning by day 1 of cycle #2 and on day 1 of every cycle thereafter, while all six conditions below have been met, patients will be evaluated for lenalidomide dose escalation.

For patients that:

- Never had a lenalidomide dose reduction due to a toxicity that was probable or definitely related to lenalidomide.
- Maintained platelet count $\geq 50,000$ at all times in the previous cycle
- Minimum ANC $\geq 1,000$ at all times in the previous cycle
- No clinically significant grade 2 or greater non-hematologic toxicities in the previous cycle
- Not yet reached the maximum daily dose of 25 mg of lenalidomide
- Are willing to undergo dose escalation of lenalidomide.
- Serum Creatinine maintained at ≤ 2 mg/dL as in initial eligibility

Then the patient's dose for lenalidomide will be increased by 5 mg per cycle for days 1-21 of a 28 day cycle. If any of the criteria are not met, then no lenalidomide dose escalations will occur during this cycle.

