5.3.1 Table 5.1 Adverse events and Dose Adjustment of drugs

Neutropenia	Grade 3 or greater on day 1 of cycle: delay and monitor CBC weekly; if resolves to \leq grade 2 within 4 weeks, resume lenalidomide with 5mg dose reduction. If grade 3 or greater during a cycle, hold lenalidomide for the remainder of the cycle. Resume with 5mg dose reduction for subsequent cycles. G-CSF or GM-CSF are not to be used to avoid dose reductions but can be used for treatment of febrile neutropenia
Febrile Neutropenia	Hold lenalidomide for the remainder of the cycle. Consider G-CSF administration until there is adequate count recovery $ANC \geq 1000/\mu L$ + absence of fever. If neutropenia resolves \leq grade 2, resume lenalidomide at 5 mg dose reduction for subsequent cycles.
Thrombocytopenia	If grade 3 or greater, hold lenalidomide for the remainder of the cycle and until platelets $\geq 50,000/\mu L$. Then resume lenalidomide at 5 mg dose reduction for subsequent cycles.
Anemia	For grade 3 or greater, hold lenalidomide for the remainder of the cycle and until hemoglobin recovers to \leq grade 2.
Fatigue (asthenia, malaise) Lenalidomide or dexamethasone	For intolerable grade 2 or grade 3-4, hold the protocol therapy thought to be probable or definitely related to the reaction until resolves to \leq grade 1, then resume protocol therapy with dose reduction of implicated protocol therapy by one dose level (5 mg for lenalidomide and/or 50% for dexamethasone).
Rash Lenalidomide	If grade 3 or greater, hold lenalidomide until resolves to \leq grade 2, then resume protocol therapy. In the instance of intolerable recurrent rash, stop implicated drug but may continue on study.
Renal insufficiency	For patients with calculated or measured GFR $<30\text{ml/min}$, lenalidomide should be held until creatinine returns to baseline
Venous Thromboembolism	All protocol should be held until the patient is adequately anti-coagulated. Patients with recurrent thrombosis despite adequate anti-coagulation should be removed from protocol therapy.
Suspected Pregnancy	Protocol therapy should be held until pregnancy is ruled out. Discontinue all protocol therapy if pregnancy is positive
Dyspepsia, gastric or duodenal ulcer, gastritis Grade 1-2 (requiring medical management)	Treat with H2 blockers, sucralfate, or omeprazole. If symptoms persist despite above measures, decrease dexamethasone dose by 1 dose level

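### Lenalidomide section 5.2.1 has no hemoglobin condition, so after a rest-of-cycle hold for grade 3+ anemia it can order a 5 mg increase where section 5.6 orders a reduction

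*Combined protocol and SAP*

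**What the plan says.** **Increase rule (5.2.1).** From day 1 of cycle 2, "while all six conditions below have been met, patients will be evaluated for lenalidomide dose escalation". If they are met, the patient's "dose for lenalidomide will be increased by 5 mg per cycle for days 1-21 of a 28 day cycle". If not, "If any of the criteria are not met, then no lenalidomide dose escalations will occur during this cycle". Three conditions matter here:

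- Prior reduction: "Never had a lenalidomide dose reduction due to a toxicity that was probable or definitely related to lenalidomide".
- Blood counts: platelets at least 50,000 and ANC at least 1,000 throughout the previous cycle.
- Other toxicity: "No clinically significant grade 2 or greater non-hematologic toxicities in the previous cycle".

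The remaining conditions are the 25 mg cap, the patient's willingness and serum creatinine. None concerns hemoglobin.

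**Hold rule (5.3.1, Table 5.1).** The anemia row reads "For grade 3 or greater, hold lenalidomide for the remainder of the cycle and until hemoglobin recovers to" grade 2 or lower. It has no attribution limit, unlike the fatigue row ("hold the protocol therapy thought to be probable or definitely related to the reaction"), and gives no resume dose. The other three hematologic rows do give one, for example thrombocytopenia: "Then resume lenalidomide at 5 mg dose reduction for subsequent cycles".

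**Restart rule (5.6).** The new cycle starts one lenalidomide level lower in either of two situations. One is that dosing was skipped for the rest of the preceding cycle. The other is that the new cycle is delayed by lenalidomide-related toxicity first met on its scheduled Day 1.

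**The concern.** A clinically significant grade 2 non-hematologic event stops an increase under 5.2.1. Anemia severe enough to require a hold does not by itself do so. The increase is worded as an instruction, not an option, so a site that follows 5.2.1 would raise the dose in the cycle after a mandatory safety hold. A site that follows 5.6 would lower it.

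The case is not contrived. Section 1.3.1 reports anemia more often with lenalidomide plus dexamethasone than with dexamethasone alone. Under the causality definitions in 10.2, an event that fits the drug's pattern but could come from another medical condition is rated possible. That is a natural rating for anemia in myeloma, and it escapes the prior-reduction condition.

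At stake is patient dosing after a hold and consistency between sites. The day 17 blood count after an increase (5.8.6, note f) would help detect a recurrence, but only once the higher dose has been given.

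**Working it through.** The protocol states no figure to reproduce. The check traces the rules using its own doses.

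**Inputs**
- Increase step: 5 mg (5.2.1).
- One lenalidomide level: 5 mg (Table 5.1, fatigue row).
- Cap: 25 mg (5.2.1).
- Phase I lenalidomide doses: 15, 15, 25 and 25 mg in cohorts 1 to 4 (5.1.1).

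**Step 1: the patient.** Below 25 mg; held for the rest of the cycle for grade 3+ anemia and recovered to grade 2 or lower; never reduced for a probable or definite toxicity; all other 5.2.1 conditions met.

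**Step 2: apply both rules at the same cycle start.**

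| Dose held | 5.2.1: dose + 5 | 5.6: dose − 5 | Gap | Ratio |
|---|---|---|---|---|
| 15 mg | 20 mg | 10 mg | 10 mg | 20/10 = 2.0 |
| 20 mg | 25 mg | 15 mg | 10 mg | 25/15 = 1.67 |
| 25 mg | not applicable (cap) | 20 mg | – | – |

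**Step 3: does attribution of the anemia settle it?** If it is rated probable or definite and 5.6 is applied first, the resulting reduction fails the prior-reduction condition and blocks the increase. If it is rated possible or lower, applying 5.6 first does not fail that condition, and the conflict remains. For the same reason, a 5 mg increase is open again one cycle later if the other conditions are then met.

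**Step 4: when does 5.6 not oppose the increase?** Only when no dosing was omitted for the rest of a cycle. Examples are anemia first found on off-drug days 22–28, or on Day 1 and judged not lenalidomide-related. The start-of-cycle criteria in 5.6 name ANC and platelets but not hemoglobin. The Table 5.1 hold until recovery still applies, but nothing in 5.6 then opposes the 5.2.1 increase.

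**Step 5: who is exposed?** Two of the four planned phase I levels start below 25 mg (cohorts 1 and 2), with 3 to 6 patients each: 2 × 3 = 6 to 2 × 6 = 12, before replacements and if both open. Lower or intermediate levels open only after two or more DLTs. The 23 added phase II patients are exposed only if the phase II lenalidomide dose is below 25 mg. The documents give no rate of grade 3 anemia, so the number affected cannot be estimated.

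**The case against.** The strongest reply is that 5.6 already lowers the dose, so nobody held for anemia would be increased. It is right that a reduction is ordered. It does not dispose of the point, because 5.2.1 also applies at that visit and no order of precedence is given.

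A reader might go further and infer that the held patient is simply due an unopposed increase, by reading the lenalidomide-related qualifier in 5.6 as covering the omission case too. The documents do not support that. The qualifier continues into toxicity newly met on the new cycle's Day 1, which cannot have caused doses to be skipped in the cycle before, and the sentence opens its second case with its own conditional. The qualifier belongs to the delay case only. After a rest-of-cycle hold, 5.6 therefore orders a reduction whatever the attribution.

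Two other safeguards deserve credit:

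- Section 5.2.2 requires a toxicity check before each dose, with modifications based on what occurred, and is not limited to non-hematologic events. An investigator would probably use it sensibly, but it names no dose and does not rank 5.2.1 against 5.6.
- The synopsis (Study Design) lets a patient continue after a lenalidomide-related hematologic DLT only with a lenalidomide reduction. With 4.2, this covers cycle 1 grade 4 anemia that is unexplained by disease and counts as a lenalidomide-related DLT. Grade 3 anemia is not a DLT, and later cycles are not covered.

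Finally, a uniform 5 mg cut written into the anemia row would be a clinical preference: 4.2 deliberately separates anemia explained by the disease. That objection stands, and the fix avoids such a cut.

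**Conclusion.** The dosing rules conflict as written; the point is minor. For the patient described, 5.2.1 and 5.6 point in opposite directions and differ by 10 mg at the same cycle start, with nothing to say which governs. An increase that 5.6 does not oppose is confined to the narrow cases in which no dosing was omitted for the rest of a cycle.

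This rests on taking the increase wording in 5.2.1 as mandatory, on one lenalidomide level being 5 mg, and on the omission case in 5.6 carrying no attribution limit.

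A reader might infer a distorted MTD or response rate. Neither is claimed: DLTs are counted in cycle 1 while increases begin at cycle 2, and nothing in the documents allows an effect on response to be sized. Patients at 25 mg are unaffected.

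**What to change.** 1. Add a condition to 5.2.1: *No grade 3 or greater anemia in the previous cycle or on day 1.* The text announces six conditions but lists seven, so the count should read eight after this addition; that is housekeeping only.
2. Add one sentence to 5.2.1: *A hold or reduction under Table 5.1 or section 5.6 overrides any increase under this section.*
3. In the anemia row of Table 5.1, cross-refer to 5.6 for the resume dose. Do not add a new attribution-free 5 mg cut there.

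The cost is a short wording amendment. No new test is needed: blood counts are already scheduled biweekly in cycles 1 to 4 and monthly afterwards (5.8.6, note e). The downside is that a few patients with disease-related grade 3 anemia would forgo one 5 mg increase in that cycle.

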5.2.2 Lenalidomide dose levels

Before each drug dose, the patient will be evaluated for possible toxicities that may have occurred after the previous dose(s). Toxicities are to be assessed according to the NCI Common Terminology Criteria for Adverse Events (CTCAE), Version 4.0. Dose modifications or delays will be done based on the toxicity experienced during a cycle of therapy or newly encountered on day one of a cycle.

5.3 Dexamethasone

Dexamethasone 40 mg orally weekly (days 1,8,15, 22) may be added if only stable disease after 3 cycles according to the IMWG response criteria (section 13-0). Dexamethasone can be reduced to 20 mg based on tolerability or if patient is 70 years or older.

5.3.1 Table 5.1 Adverse events and Dose Adjustment of drugs

Neutropenia	Grade 3 or greater on day 1 of cycle: delay and monitor CBC weekly; if resolves to \leq grade 2 within 4 weeks, resume lenalidomide with 5mg dose reduction. If grade 3 or greater during a cycle, hold lenalidomide for the remainder of the cycle. Resume with 5mg dose reduction for subsequent cycles. G-CSF or GM-CSF are not to be used to avoid dose reductions but can be used for treatment of febrile neutropenia
Febrile Neutropenia	Hold lenalidomide for the remainder of the cycle. Consider G-CSF administration until there is adequate count recovery $ANC \geq 1000/\mu L$ + absence of fever. If neutropenia resolves \leq grade 2, resume lenalidomide at 5 mg dose reduction for subsequent cycles.
Thrombocytopenia	If grade 3 or greater, hold lenalidomide for the remainder of the cycle and until platelets $\geq 50,000/\mu L$. Then resume lenalidomide at 5 mg dose reduction for subsequent cycles.
Anemia	For grade 3 or greater, hold lenalidomide for the remainder of the cycle and until hemoglobin recovers to \leq grade 2.
Fatigue (asthenia, malaise) Lenalidomide or dexamethasone	For intolerable grade 2 or grade 3-4, hold the protocol therapy thought to be probable or definitely related to the reaction until resolves to \leq grade 1, then resume protocol therapy with dose reduction of implicated protocol therapy by one dose level (5 mg for lenalidomide and/or 50% for dexamethasone).
Rash Lenalidomide	If grade 3 or greater, hold lenalidomide until resolves to \leq grade 2, then resume protocol therapy. In the instance of intolerable recurrent rash, stop implicated drug but may continue on study.
Renal insufficiency	For patients with calculated or measured GFR $<30\text{ml/min}$, lenalidomide should be held until creatinine returns to baseline
Venous Thromboembolism	All protocol should be held until the patient is adequately anti-coagulated. Patients with recurrent thrombosis despite adequate anti-coagulation should be removed from protocol therapy.
Suspected Pregnancy	Protocol therapy should be held until pregnancy is ruled out. Discontinue all protocol therapy if pregnancy is positive
Dyspepsia, gastric or duodenal ulcer, gastritis Grade 1-2 (requiring medical management)	Treat with H2 blockers, sucralfate, or omeprazole. If symptoms persist despite above measures, decrease dexamethasone dose by 1 dose level
> Grade 3 (requiring hospitalization or surgery)	Hold dexamethasone until symptoms adequately controlled. Restart and decrease one dose level of current dose along with concurrent therapy with H2 blockers, sucralfate, or omeprazole. If symptoms persist despite above measures, discontinue dexamethasone and do not resume.

Acute pancreatitis	Discontinue dexamethasone and do not resume
Edema > Grade 3 (limiting function and unresponsive to therapy or anasarca)	Diuretics as needed, and decrease dexamethasone dose by 1 dose level; if edema persists despite above measures, decrease dose another dose level. Discontinue dexamethasone and do not resume if symptoms persist despite second reduction.
Confusion or mood alteration > Grade 2 (interfering with function +/- interfering with activities of daily living)	Hold dexamethasone until symptoms resolve. Restart with one dose level reduction. If symptoms persist despite above measures, permanently discontinue dexamethasone.
Muscle weakness > Grade 2 (symptomatic and interfering with function +/- interfering with activities of daily living)	Decrease dexamethasone dose by one dose level. If weakness persists despite above measures decrease dose by one dose level Discontinue dexamethasone and do not resume if symptoms persist.
Hyperglycemia > Grade 3 or higher	Treatment with insulin or oral hypoglycemics as needed. If uncontrolled despite above measures, decrease dose by one dose level until levels are satisfactory

5.3.2 Lenalidomide dose levels

Toxicities are to be assessed according to the NCI Common Terminology Criteria for Adverse Events (CTCAE), Version 4.0. Dose modifications or delays will be done based on the toxicity experienced during a cycle of therapy.

5.4 Dexamethasone

Dexamethasone 40 mg orally weekly (days 1,8,15, 22) may be added if only stable disease after 3 cycles according to the IMWG response criteria (section 13-0). Dexamethasone can be reduced to 20 mg based on tolerability or if patient is 70 years or older.

5.5 Supportive Care

Patients will receive full supportive care while on this study. This includes blood product support, antibiotic treatment and treatment of other newly diagnosed or concurrent medical conditions. All blood products and concomitant medications such as anti-diarrheal, analgesics, anti-emetics received from the first administration of study drugs until 30 days after the final dose are to be recorded in the medical record.

All patients will receive prophylaxis with either an H-2 blocker or proton pump inhibitor while on study medications. Suggested medications included ranitidine 150 mg oral twice daily or omeprazole 20 mg oral daily or equivalent.

Patients may receive bisphosphonates at physician's discretion.

5.5.1 Thromboprophylaxis

Lenalidomide increases the risk of thrombotic events in patients who are at high risk or with a history of thrombosis, in particular when combined with other drugs known to cause thrombosis. When lenalidomide is combined with other agents such as steroids (e.g. dexamethasone, prednisone), anthracyclines (doxil, adriamycin) and erythropoietin, the risk of thrombosis is increased.

It is required that patients receive 81-325 mg of aspirin (enteric-coated is preferred) as thromboprophylaxis, equivalent or more intensive anticoagulation strategies with low molecular weight heparins or full-dose warfarin are permitted.

5.5.2 Growth factors

Prophylactic use of growth factors is not recommended.

5.6 Requirements at the beginning of each cycle

A new course of treatment may begin on the scheduled Day 1 of a new cycle if:

- The ANC is $\geq 1,000/\mu\text{L}$;
- The platelet count is $\geq 50,000/\mu\text{L}$;
- Any lenalidomide-related allergic reaction/hypersensitivity or sinus bradycardia/ other cardiac arrhythmia adverse event that may have occurred has resolved to \leq grade 1 severity;
- Any other lenalidomide-related adverse event that may have occurred has resolved to \leq grade 2 severity.

If these conditions are not met by Day 1 of a new cycle, the subject will be evaluated weekly and a new cycle of therapy will not be initiated until the toxicity has resolved as described above. Patients unable to initiate a new cycle of therapy within 4 weeks due to treatment related toxicity will be removed from study.

- If lenalidomide dosing was held during the previous cycle and was restarted with a one-level dose reduction without requiring an interruption for the remainder of the cycle, then that reduced dose level will be initiated on Day 1 of the new cycle.
- If lenalidomide dosing was omitted for the remainder of the previous cycle or if the new cycle is delayed due to lenalidomide related toxicity newly encountered on the scheduled Day 1, then the new cycle will be started with a one-level dose reduction of lenalidomide.

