4.4 Duration of Treatment

Patient can continue study treatment at the treating physician's discretion. Patients achieving at least a stable disease can continue treatment until one of the following is reached:

- Progression of disease
- Death
- Unacceptable toxicity
- Patient decision
- Treatment delay greater than 4 weeks.

Overall response will be assessed after 4, 8, and 12 cycles. If disease progression is observed at the end of Cycle 4 evaluation, all study therapy will be discontinued. In addition, study therapy will be discontinued at the time of disease progression as noted above. Otherwise patient can continue treatment until one of the above endpoints is reached.

Following the 30-day post-treatment follow-up assessment, additional evaluations will occur once per month (unless subject discontinued due to progression) until the earliest of the following events:

- Disease progression,
- The time of initiation of new therapy,
- Death or study completion.

Study completion is defined as 30 days after the last subject remaining on study medication discontinues study medication.

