5.8.6 Schedule of Events^a

Investigations	Screening	C1D3	C1D4	C1D6	C1D10	C1D17	C2D3	C3D3	C5D3	CxD3	End of Tx ^b	Follow Up ^p
History, physical examination, concomitant medication review	X	X					X	X		X	X	
Informed written consent	X											
Confirmation of disease relapse and prior treatment	X											
Skeletal survey (CT or MRI as clinically indicated) ^c	X										X	
MUGA or ECHO	X											
β-hCG ^d	X	X										
Toxicity evaluation	X	X					X	X		X	X	X
CBC / differential / platelets ^e	X	X					X	X	X	X ^f	X	
PTT, INR, TSH ^e	X											
BMP, glucose, magnesium ^e	X	X					X	X		X		
LFTs	X	X					X	X		X		
Beta 2 microglobulin ^g	X							X			X	
12-lead ECG ^h	X							X				
Serum monoclonal protein assessments ⁱ	X	X ⁱ					X ⁱ	X ⁱ		X ⁱ	X ⁱ	
24hr urine for creatinine clearance	X											
24hr urine monoclonal protein and immunofixation ^j	X	X ^j					X ^j	X ^j		X ^j	X ^j	
BM biopsy, unilateral ^k	X								X ^k		X ^k	
CT-011 Given		X					X	X	X	X		
Prescribe lenalidomide via RevAssist ^l	X											
T-cell, NK-cell, and CD14 Correlative studies ^m	X	X	X	X	X	X	X	X	X	X	X	X

CT-011 PK ⁿ		X	X	X	X	X	X				
ADA (immunogenicity) ^o	X										

- a. With the exception of PK samples, all other time points have a +/- 4 day window to accommodate weekends, holidays, and for patient convenience.
- b. Off study correlates will be done. In addition, continued T-cell correlate will be done at 1,3, and 6 months after removal from study
- c. Skeletal survey will be done at baseline and may be done at evidence of progression of disease. CT scan will be done to document size of plasmacytoma if this is the only measurable disease.
- d. Female patients of childbearing potential (FCBP, defined in section 8.5) must have a negative pregnancy test (β -hCG) as required by the RevAssist program. Lenalidomide and dexamethasone will start on day 1 of each cycle. Patients do not need to be in clinic to initiate this as all patients would have been exposed to both. Lenalidomide will be ordered for the next cycle. A pregnancy test (urine or serum β -HCG) will also be ordered at this time. Patients must have a negative β -HCG result prior to starting lenalidomide on day 1 of each cycle.

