- e. CBC d/p will be monitored biweekly in cycles 1 to 4, then monthly thereafter. Chemistry tests, including electrolytes, glucose and serum creatinine, should be performed every 2 weeks during the first 2 months of therapy and once a month thereafter. Serum electrolyte monitoring should include potassium, magnesium and calcium. PTT, INR and TSH will be checked every 2 months.
- f. CBC/d/p should also be checked on day 17 of a cycle where lenalidomide's dose has been escalated.
- g. Beta 2 microglobulin will be done after every 2 cycles and at evidence of progression of disease.
- h. Baseline and periodic ECGs should be performed during treatment as indicated in the flow chart. In patients who have ECG abnormalities, ECGs should be performed more routinely as clinically indicated. ECGs post-baseline should be performed as indicated
- i. Myeloma monoclonal protein assessments (Serum protein electrophoresis & immunofixation, immunoglobulin levels, serum free light chain assay) will be performed on day 3 of each cycle (when patients come in for CT-011 infusion) as well as off study.
- j. 24hr urine monoclonal protein assessment (Urine protein electrophoresis & immunofixation) will be performed at screening and as required for response assessment.
- k. Unilateral bone marrow (BM) biopsy will be done at baseline and at end of 4th cycle and evidence of progression for patients with non secretory multiple myeloma
- l. Lenalidomide must be prescribed through and in compliance with Celgene's RevAssist® program. Prescriptions must be filled within 7 days. Any unused lenalidomide should be returned to the patient for disposition in accordance with the RevAssist® program.
- m. T-cell, NK-cell, and CD14 correlates will be collected prior to CT-011 dosing on C1D3, C1D4, C1D6, C1D10, C1D17 and then on Day 3 of all subsequent cycles. T-cell correlates only will also be collected at 1, 3, and 6 months after discontinuation of protocol therapy.
- n. Samples for CT-011 PK determination will be collected in cycle 1 prior to CT-011 infusion, immediately at the end of the infusion, 1 hour after end of infusion, approximately 24(C1D4), 72(C1D6), 168 (C1D10) & 336 (C1D17) hrs – and just prior to next (cycle 2) infusion. Off-study correlates should be obtained at the time the patient is removed from protocol for any reason.

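### From cycle 2 the Schedule of Events dates the blood count and toxicity review to Day 3 ±4 days, although section 5.6 needs both before lenalidomide starts on Day 1

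*Combined protocol and SAP*

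**What the plan says.** **Start criteria.** Section 5.6: "A new course of treatment may begin on the scheduled Day 1 of a new cycle if" the ANC and platelet thresholds are met and lenalidomide-related events have resolved to grade 1 or grade 2, depending on the event. Otherwise the patient is seen weekly and "a new cycle of therapy will not be initiated until the toxicity has resolved as described above". Section 5.2.2 calls for a toxicity evaluation ahead of every dose. The neutropenia row of Table 5.1 (section 5.3.1) has a separate delay rule for a grade 3 or worse count found on Day 1.

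**Schedule.** In section 5.8.6 the on-treatment columns from cycle 2 are all Day 3 columns, and the CBC and toxicity rows are marked there. Footnote a says that, PK samples apart, "all other time points have a +/- 4 day window to accommodate weekends, holidays, and for patient convenience". Footnote e gives a frequency: "CBC d/p will be monitored biweekly in cycles 1 to 4, then monthly thereafter". Footnote f adds a Day 17 count in a cycle where lenalidomide has been escalated. Footnote d starts lenalidomide on Day 1 and adds: "Patients do not need to be in clinic to initiate this as all patients would have been exposed to both". The only test it ties to that dose is a negative pregnancy "result prior to starting lenalidomide on day 1 of each cycle". Appendix F leaves counts for repeat prescriptions to the prescriber's judgement.

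**The concern.** The start criteria can be applied only if someone holds a recent count and a toxicity report before the first dose of the cycle. The calendar, which sites work from, points to a day when lenalidomide is already being taken. Footnote d ties one test to the Day 1 dose, but not the counts on which section 5.6 depends. Its reason for waiving the visit is prior exposure, which says nothing about the patient's counts that week.

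At stake are doses that section 5.6 forbids, and uneven handling across the participating sites. A grade 3 or worse ANC found on Day 1 delays the cycle. The same ANC found on Day 3 falls under Table 5.1's within-cycle rule, which stops lenalidomide until the next cycle. For platelets, Table 5.1 has no Day 1 branch, so the contrast is between delay under section 5.6 and a hold under Table 5.1.

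**Working it through.** The plan gives no figure to reproduce; this is day arithmetic on a 28-day cycle with lenalidomide on Days 1–21.

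**1. Permitted days for the cycle's CBC and toxicity review** (nominal Day 3, footnote a ±4).
- Earliest 3 − 4 = Day -1; latest 3 + 4 = Day 7. Counting Day 0, that is 9 days.
- On or before Day 1: Days -1, 0 and 1, so 3 of 9. After lenalidomide has started: Days 2–7, so 6 of 9.
- This describes what is allowed, not when sites actually draw.

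**2. Doses taken before the count.** The lower figure assumes the draw precedes that day's dose.
- Day 3: 2–3 doses; 2/21 = 9.5%, 3/21 = 14.3%.
- Day 7: 6–7 doses; 6/21 = 28.6%, 7/21 = 33.3%.

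**3. Age of the last scheduled count at the next Day 1, if no early draw is made.** The next Day 1 is Day 29 of the current cycle.

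| Cycle starting | Last scheduled count | Age at Day 1 | Across the ±4 window |
|---|---|---|---|
| 2 to 5, footnote e read as every two weeks from Day 3 | Day 17 | 29 − 17 = 12 days | 8–16 days |
| 6 onward, monthly counts | Day 3 | 29 − 3 = 26 days | 22–30 days |
| 6 onward, with a footnote f draw | Day 17 | 12 days | 8–16 days |

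If the footnote e wording means twice a week, the first row falls to a few days. In the second row, a Day 3 count precedes 21 − 3 = 18 to 21 − 2 = 19 of the previous cycle's 21 doses (86–90%), so it shows little of that cycle's effect on the marrow.

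**4. Does late discovery raise or lower exposure?** Take 25 mg, grade 3 or worse neutropenia, and the 28 days from the scheduled Day 1. Recovery time is an assumption.
- Found on Day 3, then stopped for the cycle: 2–3 × 25 = 50–75 mg. Found on Day 7: 6–7 × 25 = 150–175 mg.
- Found on Day 1, delayed, restarted at 20 mg: recovery at 1 week gives 21 × 20 = 420 mg; at 2 weeks, 14 × 20 = 280 mg; at 3 weeks, 7 × 20 = 140 mg; at 4 weeks, 0 mg.
- The sign changes: with a Day 3 count, 75 < 140 at 3-week recovery but 50 > 0 at 4 weeks. No direction can be claimed.

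**The case against.** The strongest reply is that the obligation already exists. Sections 5.6 and 5.2.2 and the Day 1 rule in Table 5.1 all require evaluation before dosing. The window already admits Days -1, 0 and 1, so a site can satisfy both texts today. Footnote d waives attendance, not the counts. A low count found on Day 3 still brings an immediate hold and a 5 mg reduction, and Day 7 is an outer bound, since footnote i describes Day 3 as the day patients attend for infusion. All of this stands. It limits the point to a schedule that does not deliver its own check. It does not remove the point, because compliance depends on each site noticing that the calendar's nominal day comes after the decision it should inform.

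Several stronger readings are tempting, and the documents do not support them:

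- **That the protocol permits dosing patients who fail the criteria.** Section 5.6 forbids it. A site that gives those doses breaches section 5.6.
- **That exposure is systematically higher.** Step 4 shows either sign.
- **That late discovery changes when patients are removed.** Section 5.6 says "Patients unable to initiate a new cycle of therapy within 4 weeks due to treatment related toxicity will be removed from study" and section 4.4 lists "Treatment delay greater than 4 weeks". Neither says whether a mid-cycle hold counts as a delay. That uncertainty applies to any mid-cycle toxicity, whatever the date of the count, so it is a separate matter.
- **That the count can simply move, because section 5.1.5 sets no count threshold for CT-011.** Section 5.1.3 makes later CT-011 infusions conditional on there being no adverse event of Grade 3 or above, and a low count can be one.

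**Conclusion.** The point holds as an inconsistency between the start criteria and the calendar, and it should be fixed. From cycle 2, a site that follows the grid at nominal Day 3 gives 2–3 of 21 lenalidomide doses before the count that decides whether the cycle may start, or 6–7 at the late end of the window. From the start of cycle 6, without a footnote f draw, the most recent scheduled count is about 26 days old (22–30).

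These sizes assume that the site makes no early draw and, for cycles 2–5, depend on how footnote e is read. The documents do not allow an estimate of how many patients would pass their last scheduled count and fail on Day 1. A reader might infer that the phase I result is compromised. It is not: DLTs are counted in Cycle 1 only and the gap begins at cycle 2, so the Cycle 1 MTD is unaffected. No sample-size or error-rate figure changes.

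**What to change.** From cycle 2, state in footnotes d and e that the cycle's CBC and a toxicity review (telephone is enough) must be done, and the results reviewed, before the first lenalidomide dose. Day -1 to Day 1 would serve and already lies inside footnote a's window; an earlier opening such as Day -3 is optional. Amend footnote a so that this draw has no late side, and state that a failing result is handled by the section 5.6 delay rule. Align the CBC and toxicity rows of the grid. The mid-cycle and footnote f counts can stay at Day 17.

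Do not state that the Day 3 infusion needs no CBC. The pre-dose count should be reviewed before CT-011 under section 5.1.3, and repeated on Day 3 if it was abnormal or the site thinks it necessary.

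The cost is a short amendment, one local draw per cycle separate from the infusion visit, and possibly an occasional extra CBC on Day 3.
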